### 5.3 Methods of Minimizing Bias

Excluded bias in our collective

- No selected participants
- Both sex can be included
- Any age

Potential bias in our collective:

- Since we will search for healthy volunteers, the microbiome analysis might be slightly different to the population undergoing a hip arthroplasty surgery in an orthopedic hospital.

## 6 STUDY POPULATION

Twenty healthy male and female volunteers'  $\geq 18$  years will be recruited for this clinical study. With the results of an ongoing trial investigating the effect of skin antisepsis before hip arthroplasty, we have a perfect comparator intervention group without the PDT intervention. An expected enrolment goal is 2-4 participants per month.

### 6.1 Eligibility Criteria

#### 6.1.1 Inclusion Criteria

Patients fulfilling all of the following inclusion criteria may be enrolled in the study

Inclusion criteria:

*Healthy male and female participants  $\geq 18$  years who*

- *volunteer for the pilot study in which a routine photodynamic treatment in the Department of Dermatology will be applied and effect of skin colonization will be analyzed, and*
- *an informed consent is signed by the participant (after information about the project).*

#### 6.1.2 Exclusion Criteria

The presence of any one of the following exclusion criteria will lead to exclusion of the participant:

Exclusion criteria:

- Pregnant and lactating women

- Participants inability to follow the procedures of the study, e.g. due to language problems, psychological disorders, dementia, etc.,
- Participants taking antibiotics in the 14 days prior to the photodynamic treatment or until follow-up at 14 days
- Participants who received oral retinoid therapy within the last 6 months
- Participants who received anti-inflammatory agents as NSAR within the 14 days prior and after the PDT
- Participants taking any photosensitizing drugs within 4 weeks prior to the photodynamic treatment (PDT)
- Participants who had a history of photosensitivity disorder
- Fitzpatrick's skin phototype V-VI

## 6.2 Recruitment and Screening

Volunteers for this pilot study will be recruited by the Division of Infectious Diseases of the University Hospital Zurich with a flyer (appendix 2) as a recruitment tool (on pinboard at the University Hospital Zurich and the University Hospital Balgrist). Written informed consent will be taken under supervision of PD Dr. [name].

The participants will be informed in writing and verbal on:

- The nature, purpose and duration of, and procedure for the research project;
- Their right to withhold or to revoke their consent at any time without giving reasons;
- Their right to receive information at any time in response to further questions relating to the research project;
- Their right to be informed of results concerning their health, and their right for such information or to designate a person who is to take this decision for them;
- Measures to protect the biological material and the personal data

All participants will have enough time to decide whether to participate or not (at least 1 week). The formal consent of a participant will be obtained before the participant is submitted to any study procedure. The consent form will be signed and dated by the investigator or his designee at the same time as the participant sign. A copy of the signed informed consent will be given to the study participant. The form will be retained as part of the study records in the patient file.

There will be a financial compensation (value CHF 50.00) to the participants.

## 6.3 Criteria for Withdrawal/ Discontinuation of Participants

A participant must be withdrawn from the study if

- safety reasons of PDT (other side effects than expected, or more intense known side effects).
- participant consent withdrawal

We need a minimal 10 to 15 participants to show the proof of principle of our study. Since we ask for 20 participant we can ask for 5 other participants if we had to exclude them.

A participants who discontinued the study will be follow-up at least once after PDT treatment (3 weeks) to ask for side effects. If no intervention was done, no follow-up is needed.

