## 4 STUDY OUTCOMES

### 4.1 Primary Outcome

**Outcome 1:** Immediate effect (Same day) of photodynamic treatment in combination with surgical antisepsis on bacterial skin colonization

- Skin swabs:
  - o Bacterial growth, density, and species before and immediately after PTD with standard bacterial cultures, MALDI-TOF for bacterial identification, semiquantitative amount of bacteria with dilution bacterial plates, molecular analysis using e.g RNA seq, whole genome sequencing
- Skin biopsies
  - o Changes of sebaceous and sweat glands after PDT (Histopathology with immunostaining)

**Outcome 2.** Long-term effect (1 and 3 weeks after PDT treatment) on bacterial skin colonization in the groin after photodynamic treatment

- Skin swabs:
  - o Bacterial growth, density, and species before and immediately after PTD with standard bacterial cultures, MALDI-TOF for bacterial identification, semiquantitative amount of bacteria with dilution bacterial plates, molecular analysis using e.g RNA seq, whole genome sequencing
- Skin biopsies
  - o Changes of sebaceous and sweat glands after PDT (Histopathology with immunostaining)

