### 4.3 Safety Outcomes

Every PDT is documented as in routine clinics on a standardized protocol (see appendix 1).

Clinical signs and symptoms after PDT as adverse events. We will distinguish between:

- Mild redness and pain as to be expected (yes/no)
- Advanced redness and pain more than expected (yes/no): adverse event.
  - o "More than expected" is defined, if patients needs to take more than 1 painkiller/day
- Other signs and symptoms not expected (yes/no)

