### **7.5 Concomitant Intervention(s)**

Since we only include participants for our analysis who do not take antibiotics or NSAR in the 14 days prior to the photodynamic treatment or until follow-up at 14 days, we will inform on that issue at the screening and at each study visit. We will record it in our eCRF.

The reason for this exclusion criteria is the impact on the bacterial skin flora and on inflammation in skin histopathology.

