**8.3.3 Visit 3 (day 7±3)**

Skin scraping after skin antisepsis will be repeated 7 days later and analyzed for bacterial cultures.

In short:

- Inguinal skin scraping

- Skin antisepsis
- Inguinal skin scraping
- Punch biopsies in 5 participants
- Documentation of adverse effects

**Duration:** 30 - 60 minutes

**Location:** Department of dermatology or Infectious Diseases, University Hospital Zurich

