#### **8.3.4 Visit 4 (day 21±7)**

Skin scraping after skin antisepsis will be repeated 21 days later (study visit day 21) and analyzed for bacterial cultures.

In short:

- Inguinal skin scraping
- Skin antisepsis
- Inguinal skin scraping
- Punch biopsies in 5 participants
- Documentation of adverse effects

**Duration:** 30 -60 minutes

**Location:** Department of dermatology or Infectious Diseases, University Hospital Zurich

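### The rule on antibiotics and NSAR after PDT drops whole participants, including day-0 cultures taken before the drug

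*Combined protocol and SAP*

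**What the plan says.** **Drug rule.** Section 7.5 keeps only those in "our analysis who do not take antibiotics or NSAR in the 14 days prior to the photodynamic treatment or until follow-up at 14 days". It adds: "The reason for this exclusion criteria is the impact on the bacterial skin flora and on inflammation in skin histopathology". Use is to be recorded in the eCRF, and participants are told of the rule at screening and at each visit. Section 6.1.2 lists antibiotic use up to 14 days after PDT, and NSAR use in the 14 days after PDT, among the criteria that exclude a participant. The synopsis and section 2.7 carry the antibiotic window to day 21 instead; the NSAR window is 14 days throughout.

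**Cultures at stake.** Section 4.1 has two primary outcomes: the same-day effect of PDT with antisepsis, and the "Long-term effect (1 and 3 weeks after PDT treatment) on bacterial skin colonization in the groin after photodynamic treatment". Section 5.2 places scrapings on day 0 before PDT and again after antisepsis, then at days 7 and 21. Sections 8.3.3 and 8.3.4 confirm the later ones: "Skin scraping after skin antisepsis will be repeated 7 days later and analyzed for bacterial cultures" and "Skin scraping after skin antisepsis will be repeated 21 days later (study visit day 21) and analyzed for bacterial cultures".

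**Withdrawal and analysis set.** Section 6.3 makes withdrawal compulsory for "safety reasons of PDT (other side effects than expected, or more intense known side effects". The follow-up it then requires is "follow-up at least once after PDT treatment (3 weeks) to ask for side effects". Section 10.3.1 analyses participants who terminated the study, at most 20. Section 10.4 leaves missing outcomes missing, without imputation.

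**The concern.** Excluding people who used these drugs before PDT is ordinary eligibility and is not questioned. Use after PDT is different, because it cannot be screened at entry. That part of the rule therefore works as removal after treatment, and it removes the participant, not the sample. A drug started after the day-0 visit cannot have affected a culture taken at that visit, yet nothing in the plan keeps that culture.

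Two things are at stake. Same-day results, one of the two primary outcomes, would be discarded in a study of at most 20 people. And whether a participant counts would depend on something that happens after treatment and could be related to it: section 4.3 says that a reaction beyond what is expected "is defined, if patients needs to take more than 1 painkiller/day", and an NSAR taken for that pain would trigger the exclusion. The results decide whether a hip arthroplasty trial is planned (sections 2.1 and 5.1).

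**Working it through.** **1. Timing of drug and culture.** Set the nominal culture days (0, 7, 21) against the time of the first dose. Only cultures taken after that dose fall under the reason given in 7.5.

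| First dose after PDT | Taken before the drug | Possibly affected | Kept under 6.1.2 and 7.5 |
|---|---|---|---|
| between day 0 and day 7 | day 0 | days 7 and 21 | none |
| between day 7 and day 14 | days 0 and 7 | day 21 | none |
| antibiotic between day 14 and day 21 | days 0 and 7 | day 21 | all (none under the synopsis and 2.7) |

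In the first two rows the rule discards unaffected cultures. In the third, the 14-day version keeps a day-21 culture that the drug may have affected, while the 21-day version discards unaffected ones. Neither window matches the stated reason sample by sample.

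**2. The plan's own allowance.** Section 6.3 needs 10 to 15 participants, asks for 20, and allows 5 others in place of those excluded: 15 + 5 = 20. This concerns the number of participants. A replacement restores the count, not the cultures of the person removed.

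**3. Outer bounds on the shift.** The documents give no rate of drug use, withdrawal or negative culture, so all rates here are assumed. Let s of n participants be truly culture-negative and w be lost. If all the lost are negative, the observed rate is (s − w)/(n − w); if none are, it is s/(n − w). The last column is the exact (Clopper-Pearson) 95% interval for s/n. Section 7.1.1 gives PDT to 20 participants. The n = 10 rows apply if the 10 controls of section 5.2 are among the 20.

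| n | s/n | w | Observed rate | Largest shift (points) | Exact 95% interval |
|---|---|---|---|---|---|
| 20 | 50% | 1 | 9/19 to 10/19 = 47.4% to 52.6% | 2.6 | 27.2% to 72.8% |
| 20 | 50% | 2 | 8/18 to 10/18 = 44.4% to 55.6% | 5.6 | 27.2% to 72.8% |
| 10 | 50% | 1 | 4/9 to 5/9 = 44.4% to 55.6% | 5.6 | 18.7% to 81.3% |
| 10 | 50% | 2 | 3/8 to 5/8 = 37.5% to 62.5% | 12.5 | 18.7% to 81.3% |
| 20 | 90% | 2 | 16/18 to 18/18 = 88.9% to 100% | 10.0 | 68.3% to 98.8% |
| 20 | 70% | 5 | 9/15 to 14/15 = 60.0% to 93.3% | 23.3 | 45.7% to 88.1% |

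At 50% with 1 or 2 lost, the bounds stay inside the sampling interval. In the last two rows the upper bound falls outside it. High negative rates are relevant, since section 2.4 looks for sterile cultures after PDT and antisepsis.

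**4. Direction.** If a share d is lost, with negative rate p1 among the lost and p0 among the rest, the observed rate differs from the all-treated rate by d(p0 − p1). With p0 = 60% and p1 = 30% or 90%, this is +3 or −3 points at d = 10%, and +7.5 or −7.5 points at d = 25%. The documents do not say which sign to expect.

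**The case against.** The strongest case for the plan is that this is a descriptive pilot that wants a clean set of participants free of drugs known to alter flora and inflammation. Such use may be rare: the routine form in Appendix 1 gives paracetamol before PDT, and participants are reminded of the rule at every visit. Drug use is already recorded, 6.3 allows replacements, and 10.4 is compatible with analysing each person at the times reached. All of this stands, and it keeps the point small. It justifies leaving cultures taken after the drug out of one analysis. It gives no reason to drop cultures taken before it.

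A reader might also infer that compulsory withdrawal under 6.3 is itself an error, because it leaves days 7 and 21 without planned cultures after a stronger reaction. The documents do not support that. The study's swab is a scalpel scraping (sections 3.2 and 8.1), and each later visit has scraping, antisepsis and a second scraping. Sparing reacted skin in healthy volunteers is a legitimate trade-off. The three reaction categories in 4.3 largely match the wording of 6.3, so what is missing is a cross-reference.

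Nor can it be said that 10.3.1 removes the day-0 cultures of withdrawn participants. Section 9.4 uses the same verb for regular and premature ending, so the set may or may not mean completers. The entry in 7.4 that data collection for withdrawn participants does not apply is clerical, because 6.3 and 8.2.4 give specific rules.

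**Conclusion.** The concern holds for the drug rule. Sections 6.1.2 and 7.5 discard day-0 cultures, and in some cases day-7 cultures, that the stated reason does not touch, and they make inclusion depend on an event after PDT. The two antibiotic windows, 14 and 21 days, also need to be reconciled.

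Severity is minor. How often the rule would apply is unknown, and so are the size and direction of any bias. Two stronger statements should be avoided. One is that the results are biased in a known direction. The other is that any shift must be smaller than sampling error: that is true at an assumed 50% negative rate with 1 or 2 of 20 lost, but not at 90% with 2 lost. The figures are outer bounds on assumed rates. They apply to day 0 for participants removed by the drug rule, and for those withdrawn under 6.3 only if 10.3.1 means completers.

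**What to change.** - **7.5 (and 6.1.2):** confine the exclusion criterion to use before PDT. For use after PDT, record the date of the first dose in the eCRF, keep every culture taken before it, and show day-7 and day-21 results with and without users.
- **Antibiotic window:** use one window in the synopsis, 2.7, 6.1.2 and 7.5. Running it to the day-21 culture would fit the stated reason.
- **10.3.1:** analyse all treated participants (PDT or control antisepsis) who have a baseline culture, at each time point reached. This also keeps the day-0 cultures of participants withdrawn under 6.3.
- **Clarifications only:** state in 6.3 whether the 4.3 painkiller threshold is the trigger for withdrawal, and bring 7.4 into line with 6.3 and 8.2.4. Whether to go on scraping after a stronger reaction stays a clinical decision.

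**Cost.** No added visits or samples. Numbers will differ between time points and must be shown, there is slightly more analysis, and because the form of the statistical analysis changes, section 1.15 requires an amendment approved by the ethics committee.

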## 7 STUDY INTERVENTION

### 7.1 General Information

The following flowchart shows all steps described in the study plan:

#### 7.1.1 Study Intervention

##### Study Intervention(s) A)

Who	List of interventions
PD Dr. med. [name]	Skin antisepsis, taking swabs in 20 participants
Dr. med. [name]	Photodynamic treatment (see details below) in 20 participants Skin biopsies (substudy) in 5 participants

#### 7.1.2 Control Intervention

No control intervention in this study

## 7.2 Administration of Study Intervention

### 7.2.1 Study Intervention

Details of study Intervention	Justification
1. Inguinal skin scraping before photodynamic treatment	Baseline microbiome data
2. Natural bacterial porphyrin fluorescence photography	Baseline fluorescence photography
3. Photosensitizer application, followed by fluorescence photography Photodynamic therapy (PHT) (1x) over 15 minutes at the dermatology ward	Treatment to kill bacteria and to reduce glands in order to reduce colonization bacteria
4. Skin antisepsis in the groin, skin scraping after antisepsis	To measure bacterial colonization to know the immediate effect of PDT
5. Punch biopsy  specimen of the MAL-PDT area (immediately after PDT) and of an untreated area as a control	To analyze size and structure of glands in the skin
6. Inguinal skin scraping and punch biopsy of the MAL-PDT area after 7 and 21 days	To measure bacterial colonization to know the long-term effect of PDT

 only in 5 participants

### 7.2.2 Modification of Interventions

*Trial is not modifiable*

### **7.3 Compliance with Intervention**

There will be no compliance problem of the study participant since the intervention takes place at visits 2 and 3. No intervention by the participant is needed except reporting of adverse effects.

### **7.4 Data Collection and Follow-up for Withdrawn Participants**

Not applicable

### **7.5 Concomitant Intervention(s)**

Since we only include participants for our analysis who do not take antibiotics or NSAR in the 14 days prior to the photodynamic treatment or until follow-up at 14 days, we will inform on that issue at the screening and at each study visit. We will record it in our eCRF.

The reason for this exclusion criteria is the impact on the bacterial skin flora and on inflammation in skin histopathology.

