Outcome(s):	
Primary outcome
 
 
1. Immediate effect of photodynamic treatment in combination with surgical antisepsis on bacterial skin colonization           
 
1.1. To quantitatively evaluate bacterial density and species before photodynamic treatment and after photodynamic treatment and antisepsis skin preparation
 
 
 
2. Long-term effect on bacterial skin colonization in the groin after photodynamic treatment           
 
2.1. To quantitatively evaluate bacterial density and species before and after photodynamic treatment (7 and 21 days)
 
2.2. To evaluate changes of sebaceous and sweat glands after photodynamic treatment on skin biopsies
 
 
 
 
Secondary outcome
 
 
3. To evaluate phylogenetic similarity of the microbiota on the dermis before and three weeks following photodynamic treatment
 

Study design:	Pilotstudy, open label, single center
Inclusion / Exclusion criteria:	
Inclusion criteria
 
Healthy male and female participants <math>\geq 18</math> years who
 
 
• volunteer for the pilot study in which a routine photodynamic treatment in the Department of Dermatology will be applied and effect of skin colonization will be analyzed, and
 
• an informed consent is signed by the participant (after information about the project).
 
 
Exclusion criteria
 
 
• Pregnant and lacting women
 
• Participants with inability to follow the procedures of the study, e.g. due to language problems, psychological disorders, dementia, etc.,
 
• Participants taking antibiotics in the 14 days prior to the photodynamic treatment or until follow-up at 21 days
 
• Participants who received oral retinoid therapy within the last 6 months
 
• Participants who received anti-inflammatory agents as NSAR within the 14 days prior and after the PDT
 
• Participants taking any photosensitizing drugs within 4 weeks prior to the photodynamic treatment (PDT)
 
• Participants who had a history of photosensitivity disorder
 
• Fitzpatrick's skin phototype V-VI
 

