## 2.7 Study Population

Twenty healthy male and female volunteers'  $\geq 18$  years will be recruited for this clinical study. The study will be approved by the local ethical committee and conducted with a study nurse ([name]) and a doctoral thesis student ([name]) in collaboration with the Clinic for Dermatology at the University Hospital Zurich, with the Institute of Medical Microbiology at the University of Zurich, and with the Orthopedic University Hospital Balgrist in Zurich. An informed consent will be obtained from each participant. We will exclude pregnant and lactating women, participants taking antibiotics in the 14 days prior to the photodynamic treatment or until follow-up at 21 days, participants who received oral retinoid therapy within the last 6 months, participants who received anti-inflammatory agents within the 14 days prior and after the photodynamic treatment, participants taking any photosensitizing drugs within 4 weeks prior to the photodynamic treatment, participants who had a history of photosensitivity disorder or having a fitzpatrick's skin phototype V-V (16)

We will not include vulnerable participants

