### 5.2 Study Duration and Study Schedule

The expected duration of participant's participation is 35 days from first study visit to the last follow-up time to report side effects of photodynamic treatment. The screening visit can be any time before but at least 1 week before the first study visit. The study schedule is indicated below.

**Figure 1.** Flow chart

**Fig.1.** Study design of the PDT versus the control group

\* Only performed in 8 out of 10; \*\* only performed in 4 participants

At the day of inclusion, the voluntary participant will be informed and asked for signing the informed consent by [name] when fulfilling in- and exclusion criteria. This visit and the last visit (day 35 of the study) will be at the outpatient clinic for Infectious Diseases at the University Hospital Zurich. Demographic data (age, sex, current medications, and underlying diseases) will be noted.

Appointments for the photodynamic treatment (day 0) and the control visits (day 7 and 21) at the Department of Dermatology with Dr. [name] or at the Infectious Diseases department will be made

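### If followed, the drug-use rule in 7.5 discards cultures taken before the drug and keeps last-visit cultures taken after antibiotics used beyond day 14; the synopsis, 2.7 and 10.3.1 say something different

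*Combined protocol and SAP*

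**What the plan says.** Section 7.5 sets a rule for inclusion in the analysis: "we only include participants for our analysis who do not take antibiotics or NSAR in the 14 days prior to the photodynamic treatment". The sentence goes on: "or until follow-up at 14 days, we will inform on that issue at the screening and at each study visit". Its reason is: "The reason for this exclusion criteria is the impact on the bacterial skin flora and on inflammation in skin histopathology". Use is to be recorded in the eCRF.

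The antibiotic limit appears in three other places:

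- 6.1.2: "Participants taking antibiotics in the 14 days prior to the photodynamic treatment or until follow-up at 14 days"
- Synopsis: "Participants taking antibiotics in the 14 days prior to the photodynamic treatment or until follow-up at 21 days"
- 2.7: "participants taking antibiotics in the 14 days prior to the photodynamic treatment or until follow-up at 21 days"

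For anti-inflammatory drugs, 6.1.2 has "Participants who received anti-inflammatory agents as NSAR within the 14 days prior and after the PDT". The synopsis uses the same words, 2.7 gives the same window, and 7.5 is consistent with it. The 14 versus 21 day conflict therefore concerns antibiotics only.

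Section 5.2 plans "Appointments for the photodynamic treatment (day 0) and the control visits (day 7 and 21"), with no visit on day 14. The study plan in 8.1 and sections 8.3.3 and 8.3.4 allow ±3 days around day 7 and ±7 days around day 21. Section 4.1 makes the effect at 1 and 3 weeks a primary outcome alongside the same-day effect. Section 10.3.1 takes as its dataset the participants who terminated the study, 20 at most, and does not mention drug use.

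**The concern.** Use after PDT cannot be known at enrolment, so this part of the rule acts as a post-treatment exclusion from the analysis. It has two faults.

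First, it removes people rather than samples. The stated reason is that the drugs alter skin flora and histology. That cannot apply to a scrape taken before the drug. The day-0 scrapes, which carry the immediate effect, always precede drug use that starts after that visit.

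Second, it stops at day 14, while the last swab may be taken up to day 28. Antibiotics taken in between could suppress growth. The culture would stay in the analysis and could be credited to a lasting effect of PDT.

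In addition, 7.5 and 10.3.1 define different analysis sets, and the antibiotic limit differs between sections. Two analysts could build different datasets from the same protocol.

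**Working it through.** The plan has no figure of its own to reproduce: 10.2 gives 20 volunteers without rates, effect size or power. The check is a count of scrapes and days.

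**Inputs.** Scrapes per participant: 8.3.2 lists 3 on day 0, 8.3.3 lists 2 on day 7 and 8.3.4 lists 2 on day 21, so 3+2+2 = 7. The schedule in 5.2 has 2 on day 0 and 1 at each later visit, so 2+1+1 = 4. Visit windows: 7±3 is days 4 to 10, and 21±7 is days 14 to 28.

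**Cultures lost although taken before the drug.** Under 7.5, any use after PDT and up to day 14 removes the whole participant. Use on day 12 always falls after the day-7 visit, whose latest date is day 10.

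| Drug use | Lost under 7.5 | Of these, taken before use |
|---|---|---|
| After day 0, before the day-7 swab | 7 (5.2: 4) | 3 (5.2: 2) |
| Day 12 | 7 (5.2: 4) | 3+2 = 5 (5.2: 2+1 = 3) |

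**Antibiotic days not covered before the last swab.** Uncovered days = max(0, swab day − limit).

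| Limit | Swab day 14 | Swab day 21 | Swab day 28 |
|---|---|---|---|
| Day 14 (6.1.2, 7.5) | 0 | 7 | 14 |
| 21 days (synopsis, 2.7), read as calendar day 21 | 0 | 0 | 7 |
| 21 days (synopsis, 2.7), read as the visit itself | 0 | 0 | 0 |

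**7.5 against a sample-level rule, 7-scrape schedule.** For antibiotics on day 12, 7.5 keeps 0 scrapes; a rule by sample keeps 5 and sets aside the 2 at the last visit. For antibiotics first taken after day 14 and before a day-21 swab, 7.5 keeps all 7, including 2 taken after exposure; a rule by sample keeps 5.

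**Size per participant.** One culture that changes from growth to no growth moves the growth rate by 1/n; at n = 20 this is 1/20 = 5 percentage points.

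**Illustration on assumed rates.** The documents give no exposure rate. Suppose each of 20 treated participants has a chance p of antibiotic or NSAR use between PDT and day 14. The expected number excluded is 20p, and the chance of at least one is 1−(1−p)^20.

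| Assumed p | Expected exclusions | Chance of at least one |
|---|---|---|
| 5% | 1 | 64% |
| 10% | 2 | 88% |
| 20% | 4 | 99% |

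Each exclusion discards a valid set of day-0 cultures.

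**The case against.** The strongest reply is that 7.5 only restates eligibility, since it calls itself an exclusion criterion, and that the analysis set is fixed by 10.3.1, which excludes nobody for drug use. On that reading no early culture is lost. This stands as a reading, but it does not settle the matter. 7.5 speaks expressly of who enters the analysis, and nothing says which section prevails. The loss of cultures is therefore conditional on 7.5 being followed. If 10.3.1 is followed instead, exposed cultures from every visit stay in.

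Next, the synopsis and 2.7 cover the nominal day-21 swab on either reading, and 7.5 has use asked about at each visit and recorded, so exposure would be visible. That is also true. It narrows the forward gap to the day-14 wording and to late swabs, and recorded use is what makes the remedy cheap. But recording alone does not say what happens to the culture.

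Finally, the plan is descriptive, and excluding by sample or by participant is partly a matter of preference. Descriptive counts still depend directly on which cultures enter them.

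Two stronger readings are tempting, and the documents do not support them:

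- A reader might infer that 7.5 selectively removes the strongest reactors, because 4.3 defines an excessive reaction by painkiller use. However, 4.3 names no drug, the only analgesic in Appendix 1 is paracetamol, and 6.3 already withdraws participants with side effects more intense than expected.
- A reader might infer that one exclusion could take the study below its stated minimum by counting only 10 treated participants. The group split is in a figure not shown, 7.1.1 lists PDT in 20, and 6.3 states its minimum for participants overall and provides for 5 others.

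**Conclusion.** The point holds in limited form and should be fixed before the data are analysed. Two contradictions are plain on the text: the antibiotic limit (14 days in 6.1.2 and 7.5, 21 in the synopsis and 2.7), and whether drug-exposed participants are analysed (7.5 against 10.3.1).

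If 7.5 governs, up to 5 of 7 scrapes per exposed participant (3 of 4 under 5.2) are discarded although the drug cannot have affected them. Antibiotic use also goes uncovered for 7 days before a nominal last swab, with a range of 0 to 14 across the visit window. Under the 21-day wording the gap is nil, or at most 7 days for a day-28 swab if a calendar day is meant.

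The effect on the results cannot be sized without an exposure rate. It could be nil if nobody takes these drugs, and each altered culture at n = 20 is worth 5 points. That figure assumes 20 evaluable participants and that antibiotics can turn growth into no growth, which is the premise of 7.5 itself.

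**What to change.** State one microbiological analysis rule, in the same terms, in 7.5 and 10.3.1:

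- Keep the pre-PDT restriction.
- After PDT, keep every culture taken before the drug use.
- Set aside a day-7 or day-21 culture (both scrapes of that visit, where two are taken) when antibiotics were taken between PDT and the actual swab date.
- Keep the stated NSAR window, but without reach back to earlier samples.
- Record dates of use in the eCRF, report the number of cultures set aside at each visit, and show results with and without them.

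In 6.1.2, the synopsis and 2.7, state that use starting after PDT is handled by this rule and does not remove the whole participant from the analysis. Otherwise whole-participant exclusion survives there and contradicts the new text. State also how the rule applies to anyone sampled as a control without PDT (5.2), for whom there is no PDT date to count from.

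The sponsor must reconcile the antibiotic limits in the synopsis, 2.7, 6.1.2 and 7.5. No eligibility window is proposed here; the swab-date rule concerns only which cultures are analysed.

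Cost: an amendment with ethics committee approval, since 1.15 counts the form of statistical analysis as a substantial change, plus date fields in the eCRF. No visits or samples are added. The downside is that denominators will differ by visit, and some day-21 cultures that 7.5 as written would keep will be set aside.
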